## **3.3 Development and Clinical Evaluation of ADAPT-AST in a simulated clinical setting**

### **3.3.1 AST Decision Making Algorithm Development**

The final stage of the project will be evaluating the potential clinical and resource impact of the testing framework on the same 20% of samples used in the testing dataset above. To do this, a clinically suitable AST decision making model first will need to be developed. Comparison of a range of algorithmic approaches is likely to be required, but the aim of the first decision model trialled will be to select 7 antimicrobials for testing (the number in the standard first-line panel currently tested under existing LCL SOPs). The antimicrobials that will be initially eligible for AST selection are those for which probability calculations will be outputted, listed above in Table 2.

The first prioritisation approach trialled will be to rank antimicrobial choices in descending order of susceptibility uncertainty except for cefpodoxime and cefoxitin, then to apply an algorithm in Figure 4 to ensure that a mixture of oral and intravenous agents is tested.

[figure not shown]

Figure 4: Algorithm used to select 7 antimicrobials from the sorted shortlist.

\*Amoxicillin, Amoxicillin-Clavulanate, Aztreonam, Cefalexin, Ceftazidime, Phenoxycephalothin, Piperacillin-tazobactam.

Cefpodoxime or cefoxitin are not used as treatments in the local area, but resistance to either antimicrobial indicates a high probability of resistance mechanisms which preclude use of some beta lactams (BL) and beta-lactam-beta-lactamase-inhibitor combinations (BL-BLIC)(57,58). Therefore, the algorithm will also be designed for cefpodoxime and cefoxitin to only be tested when their susceptibility is sufficiently uncertain (a defined classification threshold will be calculated for this) and there is a chance of the affected BLs / BL-BLICs, cefpodoxime and cefoxitin all being tested as part of the panel of 7.

No additional weighting, ranking or exclusion criteria will initially be applied, but depending on evaluation based on a priori microbiology / clinical / health economic knowledge, measures may need to be taken to further steward the AST choices. These may include exclusion of certain antimicrobial choices which are less practically useful for UTI but for which resistance uncertainty may be high (e.g., teicoplanin) or algorithmic prioritisation/exclusion/weighting measures for factors such as WHO

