AWaRe class, nephrotoxicity and risk of *Clostridioides difficile* diarrhoea. Stakeholder consultation by questionnaire will help to inform these sections of the algorithm. Participants in this element of the study will be:

- General Practitioners
- Antimicrobial Pharmacists
- Medical Microbiologists
- Infectious Diseases Physicians
- Acute Medicine Physicians
- Accident and Emergency Physicians
- Bacteriology senior biomedical scientist

Invitations to participate will be disseminated by all-user trust email, with compensation offered for participant time (within sponsor allowances). Participation will be outside time dedicated for clinical care. Formal informed consent of participants will be sought in writing via email, with opportunities for participants to ask questions provided via email and Microsoft Teams. The participant consent form is enclosed in Appendix 1. Once consent has been obtained, participants will be provided with a questionnaire (enclosed in Appendix 2) asking them to rank pseudonymised antimicrobials by order of appropriateness based on several factors. These findings will be analysed by linear regression to output regression coefficients, which will be considered for incorporation into the selection algorithm.

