### **3.3.2 Outcomes**

Outcomes will be assessed and compared between the 7-result AST panels provided by ADAPT-AST algorithms and those provided by standard of care algorithms based on LCL current SOPs as of 2023, both of which will be run on every available specimen. Susceptibility information will be assessed alongside drug allergies, renal function, drug interactions to characterise results that 'should', 'could', and cannot be actioned by the clinician. Computer algorithms will be written to perform this assessment in line with the schema in Figure 5 (amoxicillin provided as an example).

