## **3.4 Economic evaluation of ADAPT-AST**

## ADAPT-AST Protocol

A decision model will be developed to estimate the cost and health outcomes associated with using ADAPT-AST to inform clinical decisions about the treatment of UTI in hospitals, compared to standard care (as observed within the Liverpool data). The introduction of ADAPT-AST is intended to allow patients to receive earlier access to appropriate therapy by better targeting the use of antibiotic susceptibility tests. This has the potential to identify early a larger set of antibiotics to which an individual is susceptible. This avoids the cost and health impacts of delayed appropriate therapy, and by expanding the choice of therapies allows clinical teams to prioritise between these therapies based on other important factors: namely toxicity profile; mode of administration; risk of AMR; and anticipated differences in efficacy.

The economic evaluation will compare the AST Decision Making Algorithms evaluated within the simulated interventional trial to standard care. A conceptual model will be developed in consultation with relevant stakeholders (e.g. clinicians who treat UTIs, microbiologists) to identify how the AST information available under different AST Decision Making Algorithms (and under standard care) is likely to influence antibiotic prescription, and how this is likely to modify costs and outcomes amongst patients treated for UTIs in UK secondary care. The conceptual model will also identify which health and cost effects of introducing ADAPT-AST should be prioritised for modelling based on their likely importance for patient health and costs. This conceptual model will then form the basis for a more detailed model protocol documenting the model structure and data sources for the quantitative model.

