## **5 END OF STUDY**

The end of study will be when analysis of the simulated interventional study data on the final ADAPT-AST algorithm version is complete, at which point an End of Study Declaration will be completed and submitted to the Sponsor. After the end of study is declared no study activity, other than final analysis of the data (following 'lock' of the study database) and report writing, will be undertaken.

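### The protocol allows several ADAPT-AST decision algorithms to be evaluated on the same 20% of specimens, without fixing beforehand which one carries the primary comparison with the SOP

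*Protocol*

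**What the plan says.** Section 3.2 splits the specimens once: a random 80% for training the susceptibility model and the remaining 20% for testing it. No third set is described.

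Section 3.3.1 turns to the rule that picks the panel of seven agents. The clinical evaluation is to run "on the same 20% of samples used in the testing dataset above". On the rule itself the section says "Comparison of a range of algorithmic approaches is likely to be required", and it specifies only a starting point: "The first prioritisation approach trialled will be to rank antimicrobial choices in descending order of susceptibility uncertainty", followed by the Figure 4 algorithm. After that, "measures may need to be taken to further steward the AST choices", through exclusion, prioritisation or weighting. These changes are to depend on an evaluation grounded in prior microbiological, clinical and health-economic knowledge. A questionnaire to health professionals yields regression coefficients "which will be considered for incorporation into the selection algorithm".

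Section 3.3.2 says outcomes are "compared between the 7-result AST panels provided by ADAPT-AST algorithms and those provided by standard of care algorithms". Section 3.3.3 then describes a one-sample exact Poisson test of ADAPT-AST, treated as a single method, against the number expected under the laboratory SOP. Section 3.4 states: "The economic evaluation will compare the AST Decision Making Algorithms evaluated within the simulated interventional trial to standard care". Section 5 ends the study when "analysis of the simulated interventional study data on the final ADAPT-AST algorithm version is complete".

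**The concern.** The primary outcome is a single endpoint, the count of 'should' results available by the day of the real first-line report. The primary comparison is not equally single. A rule that ranks agents by uncertainty and a rule weighted for AWaRe class, nephrotoxicity or practical usefulness will in general pick different panels, and so may give different counts against the SOP. If more than one version is scored on the 20%, project question 2 (whether ADAPT-AST targets testing better than current practice) has several candidate answers and no stated rule for which one counts.

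Two further effects would follow if the reported version were chosen after its result was seen. The chance of a false favourable finding would exceed its nominal level, and the reported gain would be biased upwards. This is separate from the choice of input variables for the susceptibility model in section 3.2.2: settling that would still leave several panel-selection rules in play.

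**Working it through.** **What the text fixes, side by side**

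- Number of versions: more than one is expected (3.3.1, 'likely'), and several are referred to as evaluated in the simulated trial (3.4). No number is given.
- Data for evaluation: the 20% (3.3.1). It is the only specimen set that section 3.3 names. The section does not say on which specimens candidate rules are compared or refined.
- Version tested: not named (3.3.3).
- Final version: exists (5), with no selection rule, freeze point or untouched data.

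**Inputs for the size of the effect**

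- Specimens: at least 250,000 (3.1.3). This is an estimate of available data. Section 3.1.3 mentions 80% power and p < 0.05 as an example, but gives no effect size or SD, so there is no power figure to reproduce.
- Test set: 0.20 × 250,000 = 50,000.
- Level: 0.05 two-sided, hence 0.025 in favour of ADAPT-AST.
- Assumed, because the protocol gives none: number of versions k, correlation ρ between their test statistics, paired-difference SD of 1 result per specimen, and a design effect of 1 or 2 for repeat specimens from one patient.

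**Chance of at least one false result favouring ADAPT-AST**

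For independent tests the formula is 1 − (1 − 0.025)^k:

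- k = 3: 1 − 0.975³ = 0.073
- k = 5: 1 − 0.975⁵ = 0.119

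All versions run on the same specimens against the same comparator, so positive correlation is more realistic. The values for ρ > 0 come from a simulation of 300,000 draws of equicorrelated normal test statistics:

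| k | ρ = 0 | ρ = 0.5 | ρ = 0.8 | ρ = 0.9 |
|---|---|---|---|---|
| 1 | 0.025 | 0.025 | 0.025 | 0.025 |
| 3 | 0.073 | 0.063 | 0.049 | 0.042 |
| 5 | 0.119 | 0.091 | 0.063 | 0.051 |

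For 3 to 5 versions and ρ from 0 to 0.8 the range is 0.049 to 0.119, about 2 to 5 times nominal. At ρ = 0.9 it is 0.042 to 0.051.

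**Bias from reporting the best version when none truly differs from the SOP**

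Bias = E(max z) × SE, with SE = SD × √(design effect / n).

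- SE with design effect 1: 1/√50,000 = 0.00447; with design effect 2: 0.00632.
- Best of 5, ρ = 0.5, E(max z) = 0.824: 0.0037 with design effect 1, 0.0052 with design effect 2.
- Best of 10, ρ = 0, E(max z) = 1.539: 0.0069 with design effect 1, 0.0097 with design effect 2.

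The range is therefore about 0.004 to 0.010 results per specimen, and its upper end needs ten independent versions and a design effect of 2. The bias scales with the SD: an SD of 2 doubles these figures.

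**The case against.** The strongest counter-case has four parts.

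- **The intent may be one model.** Section 3.3.1 says a suitable decision model, in the singular, must be developed before evaluation. Section 3.3.3 tests ADAPT-AST in the singular, and section 5 points to one final version. The plural in 3.3.2 is weak evidence, because the standard-of-care side is plural there too. This stands in part. The plural in 3.4 is harder to set aside, since it speaks of algorithms evaluated in the simulated trial and sets them against standard care. A final version also implies earlier ones.
- **Refinement is driven by outside knowledge.** Prior clinical knowledge and a questionnaire are the stated grounds, not the 'should' count. This stands. A reader might infer that the plan is to score many versions and declare success on the winner; the documents do not say that. They leave it possible.
- **The SAP may name the primary version.** It may, and a missing multiplicity rule alone would not be a finding. But the protocol itself fixes a two-way split and puts evaluation on the 20% with no prior freeze.
- **The numerical harm is modest.** This largely stands. Two-sided rates (0.143 and 0.226 for 3 and 5 independent versions) would overstate the risk of a false 'yes', because they also count results against ADAPT-AST. Bias among a few fixed versions is small. The ease with which small differences reach significance at 50,000 specimens would remain with a single frozen algorithm. Nothing in the documents shows that versions would differ in sign.

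The study is also retrospective, and section 3.3.4 calls for randomised studies before any deployment, which limits the consequences.

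**Conclusion.** The point holds as a cheap improvement. The protocol expects a range of decision algorithms, refers to several being evaluated in the simulated trial, uses one 20% set for evaluation, and tests ADAPT-AST without saying which version is meant or when it is fixed. The main harm is that project question 2 has no single deciding comparison. The inflated error rate (about 0.05 to 0.12 against 0.025) depends on 3 to 5 versions each being tested and on ρ between 0 and 0.8, none of which the protocol states. The bias of about 0.004 to 0.010 results per specimen depends on an SD of 1 and the assumptions shown, and is small. Repeated tuning on the 20% could add more; that is not quantified here.

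**What to change.** In sections 3.3.1 to 3.3.3, state that:

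- candidate decision algorithms are compared and refined using only the 80% training specimens, by cross-validation or an inner validation set;
- one final algorithm is frozen, with date and code version, before any version is scored against the SOP on the 20%;
- this version alone carries the primary comparison on the count of 'should' results;
- all other versions, including those carried into the economic evaluation, are reported as exploratory.

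In section 3.3.2, refer to the final algorithm in the singular for the primary outcome, and link it to the final version named in section 5. With one frozen version the chance of a false favourable result returns to 0.025. If the team wants several versions to stay confirmatory, a Holm adjustment across named versions is an option, not a necessity.

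The cost is a few sentences and one code freeze. The data are retrospective, so no new data are needed. The downside is that any version refined after the 20% has been scored can only be exploratory.

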### **3.3.2 Outcomes**

Outcomes will be assessed and compared between the 7-result AST panels provided by ADAPT-AST algorithms and those provided by standard of care algorithms based on LCL current SOPs as of 2023, both of which will be run on every available specimen. Susceptibility information will be assessed alongside drug allergies, renal function, drug interactions to characterise results that 'should', 'could', and cannot be actioned by the clinician. Computer algorithms will be written to perform this assessment in line with the schema in Figure 5 (amoxicillin provided as an example).

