## ADAPT-AST Protocol

[figure not shown]

Figure 1: Current laboratory workflows fail to make use of past information related to the patient or the patient's immediate environment to make decisions about susceptibility testing, which may lead to delays in appropriate decision making. In low prevalence AMR settings, testing contributes little to clinical care.

[figure not shown]

Figure 2: In highly-prevalent AMR settings, a second round of susceptibility testing is required before appropriate antimicrobials are identified and therapy is changed. Each additional panel of susceptibility testing typically incurs at least 24 hours of delay.

This standard practice results in the provision of susceptibility information for clinicians which is:

a) Imprecise

Some laboratories in high income settings can test very large panels of antimicrobials immediately at day one (for example, the ThermoFisher® Sensititre™ Gram Negative MIC Plate tests 22 antimicrobials), but more commonly, and particularly in low or middle income (LMIC) settings, a selected subset of antimicrobials is tested at day one to save resources (for example, the MAST URI® system used in Liverpool Clinical Laboratories [LCL] tests a 7-antimicrobial panel) (4–6). There is currently a ‘one-size-fits-all’ approach to this testing, where a standard panel of antimicrobials are initially tested against urinary pathogens. These panels do not adapt for previous resistance patterns, antimicrobial prescribing, or demographic information despite their potential impact on the likelihood of susceptibility to various agents(7).

b) Inefficient

When the standard panel tested yields no appropriate antibiotics for the clinician to use, a ‘second line’ standard panel of antibiotics will then be tested. This process unnecessarily consumes the time of laboratory staff and requires additional resources to those used to set up the initial unusable panel of antimicrobials. Lack of information related to appropriate oral or outpatient parenteral antimicrobial therapy (OPAT) treatment options delays early discharge with patients required to stay in hospital to receive high-frequency intravenous (IV) antibiotic regimens(8).

c) Inequitable

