### **3.1.3 Sample size**

The main sample size consideration is the volume of data required to train the BCI algorithm; this will be higher than the sample size required to provide 80% power to detect a significant (e.g.,  $p < 0.05$ ) difference between groups in the simulated interventional study. For the binary LR techniques like that used to develop the predictive model, however, much larger sample sizes are required to provide predictive accuracy(43). Given that a range of BCI techniques are likely to be trialled and that most of the variation will be taking place in a small proportion of samples, data pertaining to a large number of specimens will be required. All eligible patients who have grown an organism in a urine specimen during the a five year period from 17th May 2017 will be recruited for the development and testing of the predictive algorithm. This period has been chosen to provide a balance between strength of model, the amount of data available, computational power required and 'concept drift' i.e., changes in susceptibility patterns and laboratory practice over time; the most recent AST practice change in LCL was implemented 17th May 2017(44). This period will provide an estimated sample size of at least 250,000 specimens, which will pertain to fewer patients than that number as some will have had urine specimens sent more than once.

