### **3.1.5 Data Cleaning**

Once researchers have been given access to the data, cleaning of the dataset will be required because:

- Intrinsic resistance patterns will be populated in the dataset according to European Committee on Antimicrobial Susceptibility Testing (EUCAST) rules to enable proper interpretation (for

instance, amoxicillin will not be tested on most *Klebsiella* species because of intrinsic resistance, but this will be a blank in the starting dataset, which will need to be filled in with an 'R')(50)

- Organisms susceptible at increased antimicrobial exposure 'I' can be interpreted as susceptible in the context of urinary tract infection according to EUCAST rules(51). They will therefore be reclassified as 'S' to facilitate the use of binary LR (see below).
- Resistance data from multiple organisms grown in the same specimen will be inputted in the same way as for individual growth, but organisms will remain linked by pseudonymised specimen number to facilitate trial of composite 'functional' resistance of multiple organism growth as an input (i.e., if either organism in the specimen is resistant report the specimen as 'R', if both are susceptible report as 'S').
- Some data elements (for instance specimen site) will have been recorded manually and there may therefore be typographical errors that require correction to make them statistically processable.
- Assessment of data completeness will be required and strategies for managing missing data developed.
- Other data transformations may need to occur to facilitate processability or economise on computing power, e.g., feature scaling or dimensionality reduction(52).

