#### ADAPT-AST Protocol

	Pivmecillinam Trimethoprim	Temocillin Vancomycin		
--	-------------------------------	--------------------------	--	--

Table 2: The group of antimicrobials from which ADAPT-AST will select a panel of 7 to test on each urine specimen, stratified by WHO AWaRe category. Cefpodoxime and cefoxitin are also part of the classification, but they are used purely in the laboratory for resistance phenotype screening purposes in Liverpool so have been left out of category as screening antimicrobials here.

A range of different BCI techniques will need to be trialled and compared for this process using open-source R, Stan, and Python coding languages on the open-source R-studio and PyCharm proprietary integrated development software platforms. A range of different BCI techniques will need to be trialled and compared for this process. However, binary LR with Markov Chain Monte Carlo (MCMC) estimation of the posterior distribution is likely to be the most appropriate initial trial technique for this because:

- A predictive model incorporating multiple input variables needs to be developed
- A supervised BCI statistical technique can be used here because the labels of the input variables are known
- The output variable only has two possible outcomes: 'S' for susceptible and 'R' for resistant
- The output variable can be expressed as a probability of outcome 'S' or 'R'
- Parameters will need to be estimated by random sampling from a posterior probability distribution which is influenced by random variables and in which there is probabilistic dependence between samples(53,54)

Proposed models will be trained on data from a randomly selected 80% of eligible specimens from the retrospective data from between 17th May 2017 and the present. The models will be based on a consistent time frame prior to each urine specimen chosen. This is because firstly the influence of prior data on current antimicrobial susceptibility probability is likely to diminish with increasing time, and secondly it will avoid bias being introduced by more data being available for specimens at the end of the dataset(39). Different periods will be trialled for those which give the highest predictive value. Wherever possible, algorithms will be designed in a 'modular' way with intuitive exchangeable components. This will increase the potential scalability and reapplication of algorithms in other settings (e.g., LMICs) with minimal algorithm modification.

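### Section 3.3.2 compares 7-result panels on every specimen, but many results for agents outside the first-line panel were never recorded, and how those gaps are scored can decide the sign of the primary contrast

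*Protocol*

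**What the plan says.** Section 3.3.2 sets "the 7-result AST panels provided by ADAPT-AST algorithms" against panels from the laboratory's current procedures, "both of which will be run on every available specimen". The primary outcome is the number of 'should' results on the day the real first-line results were reported.

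Table 2 (Section 3.2.1) is described as "The group of antimicrobials from which ADAPT-AST will select a panel of 7 to test on each urine specimen". The first selection approach in Section 3.3.1 is to "rank antimicrobial choices in descending order of susceptibility uncertainty", followed by a step to mix oral and intravenous agents. The visible text does not limit the choice to agents with a recorded result.

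Section 1.1 says the local first-line system tests seven agents. In general terms it says a second panel follows "When the standard panel tested yields no appropriate antibiotics for the clinician to use". Section 3.1.5 shows by example that an untested agent is blank in the source data. "Intrinsic resistance patterns will be populated in the dataset", and beyond that "Assessment of data completeness will be required and strategies for managing missing data developed". Section 3.3.4 concedes that some agents will not have been tested and says the effect will be weighted while the algorithm is developed.

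**The concern.** A retrospective comparison can score only results that exist. On a specimen with first-line testing only, each ADAPT-AST choice outside the first-line panel is generally blank, so the seven-result panel that Section 3.3.2 assumes is not available there. The only remedy specific to untested agents is placed where the algorithm is built, not where the outcome is counted.

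Each natural default pushes the contrast in its own way:

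- **Untested scored as not actionable:** ADAPT-AST can at best tie on first-line-only specimens.
- **Selection restricted to recorded agents:** the two panels coincide on those specimens, so the loss from dropping a useful first-line agent is never counted.
- **Complete cases only:** the comparison shrinks mainly to specimens where the standard panel failed.
- **Filled from the prediction model:** the model under evaluation supplies part of its own outcome.

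A choice made after the results are seen could support either conclusion. The secondary outcomes share the problem, and the economic model in Section 3.4 takes susceptibility information from the same simulation.

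**Working it through.** **Inputs from the protocol.** Table 2 lists 10 Access + 10 Watch + 3 Reserve + 2 Screening = 25 agents. The first-line panel has 7, so at least 25 - 7 = 18 lie outside it. If the two screening agents are set aside and the whole first-line panel comes from the other 23, the figure is 16. The evaluation set is 20% of at least 250,000 specimens, about 50,000. The protocol states no figure for this contrast, so there is none to reproduce.

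**Inputs assumed.**

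- t: share of specimens with second-line results
- u1, u2: ADAPT-AST choices outside the first-line panel on first-line-only and on second-line specimens
- p: 'should' share among the first-line results displaced on first-line-only specimens
- r: net gain per outside choice on second-line specimens, taken as positive
- q: 'should' share credited to an untested choice

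**Formula.** Results common to both panels cancel, leaving per specimen

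contrast = t·u2·r + (1-t)·u1·(q-p).

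- Untested not actionable (q = 0): t·u2·r - (1-t)·u1·p
- Untested all actionable (q = 1): t·u2·r + (1-t)·u1·(1-p)
- Selection restricted to recorded agents: t·u2·r

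The first is negative when t/(1-t) < u1·p/(u2·r). The two extremes differ by (1-t)·u1.

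**Results.**

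| t, p, r | u1, u2 | q = 0 | q = 1 | Recorded only |
|---|---|---|---|---|
| 10%, 0.3, 0.5 | 3, 3 | 0.15 - 0.81 = -0.66 | 0.15 + 1.89 = +2.04 | +0.15 |
| 10%, 0.3, 0.5 | 1, 5 | 0.25 - 0.27 = -0.02 | 0.25 + 0.63 = +0.88 | +0.25 |
| 30%, 0.1, 0.5 | 3, 3 | 0.45 - 0.21 = +0.24 | 0.45 + 1.89 = +2.34 | +0.45 |

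The third row shows no reversal. At r = 1 and p = 0.1, 0.3, 0.5, the q = 0 scoring turns negative below t = 9%, 23%, 33% if u1 = u2, but only below about 2%, 6%, 9% if u2 = 5·u1.

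**Second check, also on assumed inputs.** A simulation of 50,000 specimens used susceptible as a stand-in for 'should'. Outside results were recorded only when at most one first-line agent was susceptible, which held for about 13% of specimens. ADAPT-AST kept two first-line agents and chose five outside. Susceptibility on an average specimen was 0.45 to 0.90 for first-line agents and 0.80 to 0.90 (better) or 0.50 to 0.65 (worse) for outside agents, with a shared specimen effect of SD 2 on the logit scale, weighted 0.7 for outside agents.

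| Outside agents | Full data | Not actionable | Complete cases | Filled from tested specimens | All actionable |
|---|---|---|---|---|---|
| Better | +0.49 | -3.20 | +1.77 | -1.22 | +1.14 |
| Worse | -0.70 | -3.37 | +0.36 | -2.62 | +0.97 |

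A true advantage can appear as a loss, and a true loss as an advantage.

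**Limits of the algebra.** It assumes that a shared agent's class does not depend on other results, which Figure 5 may contradict, and it ignores intrinsic-resistance fills. If a fraction f of the untested choices is filled, the range narrows by the factor 1 - f.

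**The case against.** The strongest reply is that this is missing-data detail that belongs in a SAP. The protocol does acknowledge the gap, and weighting during algorithm development might be meant to cover scoring too, because Section 3.3.2 has algorithms perform the classification. Figures 4 and 5 were not visible and could hold a rule. The second-line trigger in Section 1.1 is background text, not the laboratory procedure. All this stands as a limit on certainty. It does not remove the point, because Section 3.3.2 fixes a comparison that the recorded data generally cannot supply, and no visible text says how an unrecorded choice counts.

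A reader might infer more than the documents support:

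- **That reversal is likely.** The thresholds depend on u1 and u2. The expectation in Section 3.1.3 that "most of the variation will be taking place in a small proportion of samples" fits a small t, but it also fits outside choices concentrating in second-line specimens, which nearly removes the reversal in the example.
- **That the range can be expressed as many standard errors.** The simple bound on the standard deviation needs the same number of outside choices on every specimen. The comparison would also set a logical extreme against sampling error. Crediting every untested choice is itself implausible when the most uncertain agents are chosen first.
- **That r must be positive.** Figure 5 would have to show that.

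For model-based filling, the 80/20 split guards against overfitting. It does not change the fact that outside results are recorded mainly where the first panel failed.

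**Conclusion.** The point holds in a bounded form. As written, the primary contrast is not fully observed on specimens with first-line testing only, and its sign can depend on a scoring choice that the visible protocol does not make. That rests on the protocol's own statements about retrospective data, a 7-agent first panel, 25 candidates and blank untested results.

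The size is illustrative only. The q = 0 scoring runs from -0.66 through -0.02 to +0.24 across the three worked cases, and the protocol gives no second-line share, panel overlap or 'should' rate to choose among them. It cannot be said that the reported result will be wrong, or in which direction. Because the primary outcome is affected, the rule should be fixed before the evaluation set is scored.

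**What to change.** Unless Figures 4 and 5 already contain a rule, reconcile Section 3.3.2 with Section 3.3.4 by stating that:

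- a selected agent with neither a recorded nor an intrinsic-resistance result is classed as untested and, in the primary analysis, is not filled from the prediction model;
- the all-specimen contrast is reported under the scorings least and most favourable to ADAPT-AST, each by re-running the full Figure 5 classification so that dependence between agents is kept;
- results are shown separately for specimens with and without second-line results, with the number of untested selections per specimen;
- imputation is a sensitivity analysis;
- if the two scorings disagree in direction, the conclusion is limited to specimens whose outcome is observed.

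Define an available specimen, and apply the same rule to the secondary outcomes.

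The cost is protocol wording, two extra runs of the classification code and some tabulation, with no new data. The downside is a wider range and possibly a narrower headline; the range may be too wide for any conclusion about all specimens.
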